4.5 Eligibility Confirmation

Study staff must adhere to MCWCC CTO SOPs regarding eligibility review/confirmation.

No waivers of protocol eligibility will be granted. When clinical factors relating to an eligibility item are unclear or questionable, the MCW PI can only provide guidance or clarification on eligibility. Any eligibility questions should be directed to [name] at [contact].

Inclusion Criteria

1. Patients aged \geq 18 years.
2. Histologically or cytologically confirmed prostate adenocarcinoma.
3. Prior radical prostatectomy or definitive radiation.
4. Biochemically recurrent prostate cancer with PSA doubling time \leq 9 months at the time of study entry (calculated per MSKCC prostate nomogram: https://www.mskcc.org/nomograms/prostate/psa_doubling_time). Calculation of PSA doubling time should include the use of all available PSA values obtained within the past 12 months prior to randomization, with a minimum of three values separated by at least two weeks apart. The PSA values used to calculate the PSA doubling time must all be \geq 0.1 ng/mL and should be measured in the same laboratory whenever feasible.
5. Prior adjuvant or salvage radiation or not a candidate for radiation based upon clinical assessment of disease characteristics and patient comorbidities. (N/A for patients who underwent definitive radiation therapy).
6. Screening PSA $>$ 0.5 ng/mL.
7. No definitive evidence of metastases on screening imaging per the judgment of the investigator. Pelvic lymph nodes measuring 1.5 cm or less in short axis diameter are allowed. Lesions identified on imaging modalities (e.g. PSMA or choline PET) that are not visualized on CT and/or MRI or radionuclide bone scan are allowed. Equivocal lesions on bone scan should be followed up with additional imaging as clinically indicated.
8. Screening serum testosterone $>$ 50 ng/dL.
9. Eastern Cooperative Oncology Group (ECOG), Performance Status grade 0-1 or Karnofsky Performance Status \geq 70.
10. No prior JAK2 inhibitor treatment.
11. Male patients, even if surgically sterilized (i.e., status post-vasectomy), must agree to one of the following:
 - Practice effective barrier contraception and another effective method of birth control if he is having sex with a woman of childbearing potential during the entire study period and through 90 calendar days after the last dose of study agent
12. Ability to understand a written informed consent document, and the willingness to sign it.
13. Left ventricular cardiac ejection fraction of \geq 50% by echocardiogram or multigated acquisition (MUGA) scan.
14. Willing to provide blood and tissue for research analysis. (encouraged but not necessary for inclusion in trial).
15. Adequate organ function as defined by the following laboratory values at screening:
 - Serum aspartate transaminase (AST), serum glutamic oxaloacetic transaminase [SGOT] and serum alanine transaminase (ALT; serum glutamic pyruvic transaminase [SGPT]) $<$ 2.5 \times upper limit of normal (ULN).
 - Total serum bilirubin \leq 1.5 \times ULN. In subjects with Gilbert's syndrome, if total bilirubin is $>$ 1.5 \times ULN, measure direct and indirect bilirubin and if direct bilirubin is \leq 1.5 \times ULN, the subject may be eligible).

- Serum potassium \geq 3.5 mmol/L. Supplementation and re-screening is allowed.
- Estimated GFR $>$ 45 ml/min using Cockcroft-Gault equation.
- Platelets \geq 100,000/mL independent of transfusion and/or growth factors within three months prior to randomization.
- Hemoglobin \geq 9.0 g/dL independent of transfusion and/or growth factors within three months prior to randomization.
- Absolute neutrophil count \geq 500/ μ L.
- Serum albumin \geq 3.0 g/dL.
- Adequate coagulation defined by prothrombin time (PT)/international normalized ratio (INR) and PTT \leq 1x.5 ULN.

Exclusion Criteria

A potential subject who meets any of the following exclusion criteria is ineligible to participate in the study.

1. Previously treated with pacritinib.
2. Prior systemic treatment with androgen deprivation therapy and/or first-generation anti-androgen (e.g. bicalutamide, nilutamide, flutamide) for biochemically recurrent prostate cancer. Prior ADT and/or first-generation anti-androgen in the (neo)adjuvant, definitive and/or salvage setting in conjunction with radiation or surgery is allowed provided last effective dose of ADT and/or first-generation anti-androgen is \geq 12 months prior to the date of randomization and the total duration of prior therapy is \leq 36 months.
3. Prior treatment with CYP17 inhibitor (e.g., ketoconazole, abiraterone acetate, galeterone) or next-generation androgen receptor antagonist including apalutamide or enzalutamide.
4. Prior chemotherapy for prostate cancer
5. Use of 5-alpha reductase inhibitor within 42 days prior to randomization.
6. Use of investigational agents within 28 days prior to randomization.
7. Use of other prohibited medications within seven days prior to Cycle 1 Day 1 on study (see Appendix 3 and 4 for list of prohibited medications).
8. Systemic treatment with a strong CYP3A4 inhibitor or a strong CYP450 inducer within 14 days prior to treatment Day 1 (Appendix 3 and Appendix 4, respectively)
9. Prior bilateral orchiectomy.
10. Uncontrolled hypertension.
11. Baseline severe hepatic impairment (Child-Pugh Class B & C).
12. An intercurrent illness that is not controlled, such as active infection, psychiatric illness/social situations that would limit compliance with study requirements.
13. Any chronic medical condition requiring a higher dose of corticosteroid than an equivalent of 10 mg prednisone/prednisolone per day.
14. Significant recent bleeding history, as defined as NCI CTCAE grade \geq 2 within three months prior to treatment Day 1, unless precipitated by an inciting event (e.g., surgery, trauma, or injury)
15. Systemic treatment with medications that increase the risk of bleeding, including anticoagulants (warfarin, direct oral anticoagulant, etc.), antiplatelet agents (except for aspirin dosages of \leq 100mg/day), vascular endothelial growth factor (anti-VEGF) agents, and daily use of COX-1 inhibiting nonsteroidal anti-inflammatory agents (NSAIDs) within 14 days prior to treatment Day 1.
16. Systemic treatment with medications that can prolong the QT interval within 14 days prior to treatment Day 1. Shorter washout periods may be permitted with the approval of the PI, provided that the washout period is at least five half-lives of the drug prior to treatment Day 1.
17. Any history of CTCAE grade \geq 2 cardiac conditions within six months before

Subject Initials: _____ Subject Study ID: _____

treatment Day 1. Patients with asymptomatic grade 2 non-dysrhythmia cardiovascular conditions may be considered for inclusion, with the approval of the PI, if stable and unlikely to affect patient safety.

18. QT corrected by the Fridericia method (QTcF) prolongation >450 ms or other factors that increase the risk for QT interval prolongation (e.g., heart failure, hypokalemia [defined as serum potassium <3.0 mEq/L that is persistent and refractory to correction]), or history of long QT interval syndrome.
19. New York Heart Association Class II, III, or IV congestive heart failure (Appendix 7).
20. Any active GI or metabolic condition that could interfere with absorption of oral medication.
21. Active or uncontrolled inflammatory or chronic functional bowel disorder such as Crohn's disease, inflammatory bowel disease, chronic diarrhea, or chronic constipation.
22. Other malignancy within three years prior to treatment Day 1, other than curatively treated basal cell or squamous cell skin or corneal cancer; curatively treated carcinoma in situ of the cervix; or in situ breast carcinoma after complete surgical resection.
23. Uncontrolled intercurrent illness, including, but not limited to, ongoing active infection, psychiatric illness, or social situation that, in the judgment of the treating physician, would limit compliance with study requirements.
24. Known seropositivity for human immunodeficiency virus.
25. Known active hepatitis A, B, or C virus infection.

I have reviewed all inclusion and exclusion criteria and confirm the subject is eligible."

(CRC Signature)

(Date)

(Investigator/Enrolling Physician Signature)

(Date)

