
PERSIST-2 was the second phase 3 study of pacritinib, comparing the efficacy of 400 mg QD and 200 mg BID with the best available therapy, including ruxolitinib, in patients with PMF, PPV-MF, or PET-MF and thrombocytopenia (baseline platelet count $\leq 100,000/\mu\text{L}$). Patients previously treated with JAK2 inhibitors were included. There were no exclusion criteria based on platelet count. Three hundred eleven patients (311) were randomized in a 1:1:1 ratio to the three treatment arms. Due to Full Clinical Hold on February 8, 2016, only 211 of the accrued patients were evaluable in the ITT (efficacy) population, having been randomized with sufficient time to reach the Week 24 evaluation window, thus limiting the power to detect differences in the efficacy endpoints.

PERSIST-2 demonstrated a statistically significant improvement in the coprimary endpoint comparing the pooled pacritinib arms with the BAT arm for the percent of pacritinib-treated patients achieving a $\geq 35\%$ reduction in spleen volume at Week 24 compared to baseline (SVR response), as assessed by centrally read MRI or CT imaging, compared to best available therapy (18.1% vs. 2.8%, $p=0.0011$). More patients in the pooled pacritinib had improved MF-related symptomatology, meeting the predefined TSS response definition ($\geq 50\%$ reduction at Week 24 compared to baseline, as assessed by MPN-SAF TSS 2.0, TSS response) than those treated with BAT, but this trend in the second co-primary endpoint was not statistically significant (24.8% vs. 13.9%, $p=0.791$). Comparing the individual pacritinib treatment arms to BAT, SVR response was nominally significant for BID (21.6%) vs. BAT ($p=0.0007$), and for QD (14.7%) vs. BAT ($p=0.0173$).

Unlike the pooled coprimary analysis, the BID arm had nominal significance for TSS response vs. BAT (32.4% vs. 13.9%, $p=0.0106$), but the QD arm did not (17.3%, $p=0.6524$). Exploratory analyses most relevant to the current study showed that in comparison with the ruxolitinib-treated

BAT patients, more pacritinib-treated patients achieved the SVR response than patients treated with either ruxolitinib or other BAT agents (QD 11/75, 14.7%; BID 16/74, 21.6%; ruxolitinib 1/32, 3.1%; other BAT 1/40, 2.5%). Similarly, more pacritinib 200 mg BID (but not 400 mg QD) patients achieved the MPN-SAF TSS2.0 response (pacritinib 24/74, 32.4% vs. ruxolitinib 6/32, 18.8%), despite the increased effect of ruxolitinib compared to all other BAT patients (4/40, 10%).

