The most commonly (>10% of all subjects) reported treatment-related TEAEs by the preferred term, were in the SOC of gastrointestinal disorders including diarrhea (62%), nausea (31%) and vomiting (18%), and the SOC of blood and lymphatic system disorders, including thrombocytopenia (16%) and anemia (15%). While GI-related events were common, they were generally reversible, of low grade, and rarely led to treatment discontinuation. The potential risk of hypersensitivity reaction with pacritinib is low. Pacritinib is contraindicated in patients with a known hypersensitivity to the active substance or any of the excipients. Potential mechanisms include an immune-mediated response to pacritinib or any of the excipients of the product.

Summary of the PAC203 Phase 2 Dose-Finding Study in Myelofibrosis

The fully enrolled phase 2 component of Study PAC203 is a dose-finding study in patients with primary or secondary MF (Dynamic International Prognostic Scoring System [DIPSS] risk score of Intermediate-1 to High Risk) who experienced intolerance or treatment failure with ruxolitinib. The patient population in Study PAC203 was selected in recognition of safety concerns concerning pacritinib that were brought to light during the PERSIST-1 and -2 studies to balance the potential for risk with the unmet medical need in patients who failed to achieve or maintain benefit from the only approved agent for MF.

Patients who are refractory to ruxolitinib are likely to have high molecular risk disease and poor survival (median: 13 to 14 months) (Newberry et al 2017; Kuykendall et al 2018; Pacilli et al 2018). As such, these patients have a lower likelihood of achieving SVR and overall poor prognosis. Enrollment was not restricted based on platelet count. The primary objective of the study is to determine the optimal dosage of pacritinib, spanning the dose-response curve for safety and efficacy established in previous phase 1/2 clinical studies and the phase 3 PERSIST-1 and -2 studies.

Patients were randomized 1:1:1 to 200 mg pacritinib BID, 100 mg pacritinib BID, or 100 mg pacritinib QD, and randomization was stratified by geographic region and baseline platelet count. A total of 165 patients were randomized in the phase 2 portion of Study PAC203, and 161 (97.6%) patients received any treatment with pacritinib. Median platelet count was 55,000/ μ L and 76% met criteria for ruxolitinib failure, 73% for ruxolitinib intolerance, and 50% for both.

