5.2.2 Dosage Management Guidelines for Hematologic Toxicity and Related Complications

Hematology parameters, including CBC, differential, will be evaluated at regular intervals during the study. These parameters should be monitored more frequently if clinically required. Unscheduled local laboratory test results may be used for the assessment and management of patients in real-time.

Table 1 indicates the required dose interruptions and modifications for hematologic toxicities and complications such as hemorrhage and febrile neutropenia that are treatment related. Of note, if more than one toxicity is experienced simultaneously, the higher-grade toxicity should determine the dose interruption/modification. Treatment-related toxicities are those that are considered at least possibly related to study drug.

Table 1. Treatment Toxicity and Dosage Management: Hematologic Toxicities and Related Complications

Event	CTCAE Grade	Management/Action
Thrombocytopenia	For patients starting treatment with baseline (Day 1) grade 1 thrombocytopenia who have treatment-related ≥ 1 grade decrease in platelets	Hold pacritinib for up to 10 days until recovery of platelet count to grade ≤ 1 or baseline. After recovery, restart at 50% of the prior dose. If thrombocytopenia recurs at the 100 mg BID dose level, discontinue pacritinib.
Hemorrhage	Treatment-emergent hemorrhage Grade 2	Hold pacritinib for up to seven days until hemorrhage resolves. Restart with a 50% dose reduction. If event recurs, discontinue pacritinib
	Grade 3	Discontinue pacritinib.
	Grade 4	Discontinue pacritinib.
Neutropenic infections, including neutropenic sepsis	Grade 2	Hold pacritinib for up to seven days and start at 50% of the dose once

		resolved (100 mg BID). If toxicity recurs discontinue pacritinib
Grade 3		Discontinue pacritinib
Grade 4		Discontinue pacritinib

Coagulation Testing

Coagulation testing will include PT, INR, PTT, at screening. Additional coagulation testing should be done as clinically indicated.

These results will be taken into account, together with baseline platelet counts and prior medical history of bleeding, to help guide ongoing hematologic monitoring of platelet counts and clinical monitoring for bleeding. Pacritinib dosage modifications will be implemented for clinically significant AEs identified with this testing per the guidelines in Table 5.

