Bleeding: Pacritinib may increase the risk of bleeding. Reports of serious bleeding events, including life-threatening and fatal events, have been reported. These bleeding events were generally without lasting sequelae, although life-threatening and fatal events of hemorrhage, including intracranial hemorrhage, were observed more frequently in pacritinib-treated patients compared with BAT patients. Risk factors for bleeding with pacritinib may include prior bleeding events and anti-platelet and anti-coagulant medications in addition to severe thrombocytopenia. Concomitant use of drugs affecting hemostasis, such as aspirin and other antiplatelet agents, other anticoagulants, heparin, and thrombolytic agents, may increase the risk of bleeding. Refer to the protocol for guidance on dose modifications for pacritinib-related bleeding events.

Cardiac: QTc prolongation has been observed in patients treated with pacritinib. Prior to initiating treatment with pacritinib, patients should undergo an ECG to establish baseline QTc and an echocardiogram (or other appropriate methodology) to establish baseline left ventricular ejection fraction; patients should be monitored periodically for changes in their QTc. Pacritinib should not be used in patients with uncontrolled cardiac dysrhythmias, QTc prolongation >450 ms, or other factors that increase the risk for QT prolongation (e.g., heart failure, hypokalemia, hypomagnesemia, or a history of long QT interval syndrome). Caution should be used when co-administering other medicinal products with the potential to elongate QT interval. Ejection fraction should be monitored at baseline, after one month on treatment, after three and six months on treatment, and every six months thereafter; pacritinib dose should be modified if significantly reduced ejection fraction is detected. Additional ECG and ejection fraction assessments should be performed as clinically indicated. Refer to the protocol for guidance on dose modifications for pacritinib-related QTc prolongation.

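### The platelet entry limit is written per mL, a thousand times below the per-microlitre counts used elsewhere, so as written it excludes almost nobody

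*Combined protocol and SAP*

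**What the plan says.** Section 4.5 (Eligibility Confirmation), inclusion criterion 15, lists the laboratory values that define adequate organ function at screening. The platelet item requires at least "100,000/mL independent of transfusion and/or growth factors within three months prior to randomization". Two bullets further down, the neutrophil item reads "Absolute neutrophil count \geq 500/ μ L".

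The protocol summary repeats the neutrophil limit per microlitre but gives no platelet number, only a general requirement for adequate organ function. None of the exclusion criteria sets a platelet count. Criterion 15 is therefore the only numeric platelet limit at entry.

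The list works as a form: the coordinator and the enrolling physician sign that all criteria have been reviewed and met. The section also states "No waivers of protocol eligibility will be granted".

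Section 1.5.4 gives platelet counts per microlitre: the PERSIST-1 subgroup cut-offs, the PERSIST-2 entry threshold and, for PAC203, "Median platelet count was 55,000/ μ L".

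**The concern.** A count per mL and a count per microlitre differ by a factor of 1,000, and the same numeral, 100,000, appears in this protocol with both units. If the per-mL figure is applied as written, men with severe thrombocytopenia satisfy the criterion.

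That matters for this drug. Section 7.7 reports clinically relevant platelet decreases on treatment, as well as serious, life-threatening and fatal bleeding, and says: "Risk factors for bleeding with pacritinib may include prior bleeding events and anti-platelet and anti-coagulant medications in addition to severe thrombocytopenia". Section 1.5.4 reports a full clinical hold prompted in part by fatal intracranial hemorrhage, and grade 3 or 4 thrombocytopenia in 20.5% of PAC203 patients.

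The dosing rules also appear to assume an entry limit that keeps low counts out. The thrombocytopenia row of Table 1 (Section 5.2.2) begins "For patients starting treatment with baseline (Day 1) grade 1 thrombocytopenia who have treatment-related" and makes no provision for a worse baseline. The literal limit would let such patients in.

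**Working it through.** The plan derives no figure for this limit, so there is nothing to reproduce. The check is a unit conversion followed by a comparison with the document's own counts.

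**Inputs**

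- Platelet limit as written: 100,000 per mL (Section 4.5, inclusion criterion 15).
- Neutrophil limit: 500 per microlitre (same list).
- PERSIST-2 entry threshold for thrombocytopenia: 100,000 per microlitre or less (Section 1.5.4).
- PERSIST-1 subgroup cut-offs: below 50,000 and below 100,000 per microlitre (Section 1.5.4).
- PAC203 median platelet count: 55,000 per microlitre (Section 1.5.4).

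**Conversion**

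Limit per microlitre = limit per mL ÷ 1,000.

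- As written: 100,000 ÷ 1,000 = 100 per microlitre. In litres, 100 × 10⁶ = 10⁸ per L, or 0.1 × 10⁹/L.
- The same numeral per microlitre: 100,000 × 10⁶ = 10¹¹ per L, or 100 × 10⁹/L.
- Ratio: 100 ÷ 0.1 = 1,000.

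**Comparison with the document's own platelet counts**

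| Reference in Section 1.5.4 | Per microlitre | Multiple of the written limit (100 per microlitre) |
|---|---|---|
| PERSIST-2 entry threshold | 100,000 | 1,000 |
| PAC203 median | 55,000 | 550 |
| PERSIST-1 lower subgroup cut-off | 50,000 | 500 |

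A patient at any of these counts, which the protocol uses to mark or describe low platelets, passes the written criterion by a factor of at least 500.

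**Does another passage correct the unit?** No. The synopsis has no platelet number, the exclusion criteria have none, and Section 7.7 requires baseline platelet testing without setting a limit.

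**The case against.** The strongest objection is that this is a typographical slip that no one would act on. The numeral 100,000 appears elsewhere in the protocol as a per-microlitre platelet cut-off, Table 1 fits that reading, and Section 4.5 lets the principal investigator clarify an unclear item even though waivers are barred. This has force as to practice: staff may well read the limit as per microlitre. It does not repair the text. The signed criterion and any audit refer to what is written, and case-by-case clarification does not replace a correct criterion.

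A second objection is that the whole point rests on one character in text extracted from a PDF, where a micro sign could have been misread as an m. The text alone cannot rule this out. The micro sign was read correctly for neutrophils in the same list, which makes a misreading less likely, and a look at the source page settles it.

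Third, other safeguards limit bleeding risk. Exclusion 14 covers recent significant bleeding, exclusion 15 covers anticoagulants and most antiplatelet agents, Section 7.6 says that patients with active bleeding should not start, and blood counts are repeated on treatment. These stand, but none sets a platelet minimum at entry.

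Fourth, the 550-fold comparison uses a myelofibrosis cohort enrolled without a platelet restriction, while this trial enrols men with biochemically recurrent prostate cancer and no prior chemotherapy for it. That is fair. The figure is illustrative, and the documents give no platelet distribution for the trial population, so the number of men who might be wrongly admitted cannot be estimated.

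**Conclusion.** The concern holds. As written, the only numeric platelet limit at entry is 100 per microlitre, exactly 1,000 times lower than the same numeral in the unit used for the other counts in the document. At that level the criterion excludes essentially no one.

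The factor of 1,000 is exact and rests on no assumption beyond the unit having been read correctly from the PDF. That the criterion excludes almost nobody is inferred from the protocol's own platelet counts in low-platelet populations, not from data on the men this trial enrols. The finding concerns the written criterion. It does not show that any ineligible patient was treated, it has no bearing on the type I error, power or sample size, and it takes no position on which platelet threshold is clinically right.

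**What to change.** Check the source page. If it shows the per-mL unit, reconcile inclusion criterion 15 with the per-microlitre unit used for neutrophils in the same list and for platelets in Section 1.5.4, and have the sponsor confirm the intended limit. Check whether the case report form carries the same unit; it is not among the documents, so this is unknown.

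In the same edit, proofread the PT/INR and PTT limit in criterion 15. Its multiple of the upper limit of normal is garbled in the extracted text, whereas the protocol summary states it legibly as 1.5 times. This too may be a reading fault and should be checked on the source page.

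The cost is one unit and one line of proofreading in a protocol amendment, plus the matching change to the case report form if it is affected. No analysis or design figure changes.
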